5. To estimate incidence rate ratios for venous and arterial thromboembolic events among patients with COVID-19 and different SARS-CoV-2 vaccine doses compared to the background population, using incidence rates estimated in objectives 1 to 3.

Study type: population-level cohort

Study population:

- 1) Pre-pandemic cohort to calculate background rates of venous and arterial thromboembolic events in the general population (year 2017-2019).
- 2) People with COVID-19 during the time when OMICRON was the dominant variant (coded or test positive). All participants are required to be visible in the data source since 1st January 2020 to have full records on infection and vaccination history.
- 3) People vaccinated against SARS-CoV-2 (+/- during the period when OMICRON was the dominant variant). All participants are required to be visible in the data source since 1st January 2020 to have full records on infection and vaccination history.

For all cohorts, individuals with recent VTE or ATE event (defined as having a diagnosis of VTE or ATE within 183 days prior to index date, with sensitivity analysis of using any time prior and 91-days as wash-out periods.) will be excluded.

	Phase II C3-001 – Study Protocol	
	Author(s): [name], [name]	Version: v3.1
		Dissemination level: public

Analysis:

Standardized incidence rate ratio (SIR) compared to the background population will be estimated using indirect standardization.

Cohorts will be stratified by prior COVID-19 infection occurrence and prior SARS-CoV-2 vaccination (COVID-19 and vaccine cohorts only), age, sex. All cohorts will additionally be stratified by whether patients are immunocompromised on the index date.

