	
shortest dosing schedule for primary vaccination series in the participated databases (SIDIAP in Spain)
 
 whether the vaccination record is 1st, 2nd, 3rd or 4th dose. 
Objective 4: Persons requiring intensive services during a hospitalisation with COVID-19 during the Omicron period will have:
 
 intensive services initiated during a hospitalisation. 
Objective 5: same as objective 1-4

Exposure:	
Objective 1: N/A
 
Objective 2: SARS-CoV-2 infection
 
Objective 3: Vaccination against SARS-CoV2 infection
 
Objective 4: Incidence VTE or ATE, or worsening severity after SARS-CoV2 infection
 
Objective 5: SARS-CoV2 infection and Covid-19 vaccines

Comparator:	
Objective 1 – 3 are descriptive incidence rate, not applicable.
 
Objective 4: No incidence VTE or ATE, or worsening severity after SARS-CoV2 infection
 
Objective 5: background population

Outcome:	
1. Venous thromboembolic events
 
In the primary analysis, venous thromboembolic events will be identified by diagnostic codes for pulmonary embolism or deep vein thrombosis.
 
2. Arterial thromboembolic events
 
In the primary analysis, arterial thromboembolic events will be identified by diagnostic codes for an acute myocardial infarction or acute ischemic stroke.

Time (when follow up begins and ends):	
Objective 1: follow-up will begin on January 1st 2017 or 365 days of prior history and continue up until the first of: outcome of interest, loss to follow-up, death or December 31st 2019.
 
Objective 2: follow-up will begin on their index date and continue up until the first of: outcome of interest, loss to follow-up, death, or either 30-, 60-, 90- or 180-days after the index date (depending upon the follow-up time period of interest).
 
Objective 3: follow-up will begin on their index date and continue up until the first of: outcome of interest, loss to follow-up, death, or

	Phase II C3-001 – Study Protocol	
	Author(s): [name], [name]	Version: v3.1
	Dissemination level: public	

	either 30-, 60-, 90- or 180-days after the index date (depending upon the follow-up time period of interest).
Setting:	Inpatient and outpatient setting using data from the following datasources: IPCI (NL), SIDIAP (Spain), IQVIA Germany (Germany), Estonian Biobank – via Utartu (Estonia) and CPRD GOLD (UK). Inpatient information is only available in SIDIAP.

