8.4 Follow-up

For cohort 1, follow-up will begin on January 1st 2017 and continue up until the first of: outcome of interest, loss to follow-up, death or December 31st 2019. For cohorts 2 to 5, follow-up will begin on their index date and continue up until the first of: outcome of interest, end of observation period, end of data availability, death, or either 30-, 60-, 90- or 180-days after the index date (depending upon the follow-up time period of interest).

Table 2: Operational Definition of Time 0 (index date) and other primary time anchors

Study population name(s)	Time Anchor Description (e.g. time 0)	Number of entries	Type of entry	Washout window	Care Setting ¹	Code Type	Diagnosis position	Incident with respect to...	Measurement characteristics / validation	Source of algorithm
Background population (cohort 1*)	January 1 st 2017 or after when they have 365 days of prior history	Multiple	General population	n/a	n/a	n/a	n/a	n/a	n/a	n/a
SARS-CoV-2 infection cohort (cohort 2*)	Date of test for the positive test result for SARS-CoV-2, or date of clinical diagnosis of COVID-19	Multiple	incident	No covid-19 infection within 3 months prior	OP	SNOMED codes (see appendix)				
hospitalised with COVID-19 cohort (cohort 3*)	Date the date of hospital admission	Multiple	incident	No hospitalization within	IP	SNOMED codes (see appendix)				

This document represents the views of the DARWIN EU® Coordination Centre only and cannot be interpreted as reflecting those of the European Medicines Agency or the European Medicines Regulatory Network.

	Phase II C3-001 – Study Protocol	
	Author(s): [name], [name]	Version: v3.1
	Dissemination level: public	

				3 month s prior						
Intensive care service cohort (cohort 4*)	Date of the following depends on availability in data, descend priority: 1.)Date of intensive care service (mechanical ventilation, tracheostomy, or extracorporeal membrane oxygenation (ECMO)); 2.)Date of ICU admission; 3.)Date of hospital admission.	Multiple	incident	n/a	IP	SNOMED (see appendix)	n/a	Covid-19 hospitalized	n/a	n/a
Vaccinated cohort (cohort 5*)	date of vaccination record	Multiple	n/a	21 days	OP	RxNorm codes (see appendix)				

*Cohorts number as described in 8.5 study population with inclusion and exclusion criteria.

¹ IP = inpatient, OP = outpatient, ED = emergency department, OT = other, n/a = not applicable

Description of the different items from the table can be found below:

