Study population name(s): A brief text descriptor naming the study population that is identified for a primary or secondary analysis (e.g. exposed, comparator, pregnant women, patients with diabetes)

Time anchor description: A brief text description of the criterion used to define the time anchor, including at least one entry to define time 0, the point at which the patient enters the cohort (e.g. date of incident dispensation of Drug X, date of heart failure diagnosis, last menstrual period)

Number of entries: Indicate whether patients are allowed to enter the study population only once or multiple times (e.g. single entry, multiple entry)

Type of entry: Indicate whether the criterion for entry to the study population reflects an incident, prevalent, or other condition.

	Phase II C3-001 – Study Protocol	
	Author(s): [name], [name]	Version: v3.1
		Dissemination level: public

Washout window: If entry to the study population is defined as incident, use bracketed numbers representing time intervals anchored on a primary anchor (usually time 0) to specify the washout window. For example, [-180, -1] would reflect a washout window of 180 days prior to time 0, where the brackets indicate that the window is inclusive of the endpoints.

Care setting: Specify the care setting(s) that are used in the algorithm to define the time 0 (or other primary anchor) criterion. For example, IP = inpatient, ED = emergency department, etc.

Code type: Specify the type(s) of clinical codes that are used to define the time 0 (or other primary anchor) criterion.

Diagnosis position: If the algorithm to define the time 0 (or other primary anchor) criterion used inpatient codes, specify whether the algorithm restricts to primary diagnosis codes (indicating that the code is the primary reason for the encounter) or allows codes in secondary or any position (e.g. primary, secondary, any, n/a)

Incident with respect to: If the type of entry is defined as incident, provide a brief text description of what the patient is required to be incident to. For example, when identifying incident users of Drug X (oral formulation only), the investigator may wish to require that patients be incident with respect to Drug X (oral formulation) as well as Drug X (intravenous formulation) and Drug Y. This would be operationalized as having no record of exposure to any of these drugs during the specified washout period.

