Covid-19 intensive care use (cohort 4)	intensive services initiated during a hospitalisation as described in the “covid-19 hospitalized” criterion	before	During hospitalization	Intensive care	SNOMED	n/a	Individuals who met the “covid-19 hospitalized” criteria	n/a	n/a
Covid-19 vaccinated (cohort 5)	a vaccination record identified by brand (with the index date the date of vaccination record)	before	n/a	Primary care	RxNorm	n/a	All individuals within the selected databases	n/a	n/a

¹ IP = inpatient, OP = outpatient, ED = emergency department, OT = other, n/a = not applicable

² Specify whether a diagnosis code is required to be in the primary position (main reason for encounter)

Table 4. Operational Definitions of Exclusion Criteria

Criterion	Details	Order of application	Assessment window	Care Setting¹	Code Type	Diagnosis position²	Applied to study population^s	Measurement characteristic^{s/}	Source for algorithm
Prior covid-19 (cohort 2-4)	have no positive test result for SARS-CoV-2 or clinical diagnosis of COVID-19 within 3 months prior to the index date.	After	[-91,0]	OP,IP	SNOMED, RxNorm	n/a	SARS-CoV-2 infected, hospitalized (cohorts 2, 3, 4)	n/a	n/a

	Phase II C3-001 – Study Protocol	
	Author(s): [name], [name]	Version: v3.1
	Dissemination level: public	

Hospitalization (cohort 3)	have no diagnosis of COVID-19 or a positive test result for SARS-CoV-2 between 3 months and 3 weeks prior to index date. Have no COVID-19 hospitalisation within 3 weeks prior to the index date.	After	Covid-19 [-91,-21]; Hospitalization [-21,0]	IP	SNOMED	n/a	Covid-19 hospitalized (cohorts 3, 4)	n/a	n/a
Vaccinated (cohort 5)	No vaccine records in the 21 days prior to index vaccine	after	[-21 , 0]	OP	RxNorm	n/a	Vaccinated (cohort 5)	n/a	n/a
Prior outcomes all cohorts)	Exclude people with the outcome of interests during the 183 day prior to index. (primary analysis, different washout period will be applied in sensitivity analysis)		[-183,0]	IP, OP	SNOMED	n/a	(cohorts 1-5)	n/a	n/a

1 IP = inpatient, OP = outpatient, ED = emergency department, OT = other, n/a = not applicable

2 Specify whether a diagnosis code is required to be in the primary position (main reason for encounter)

Criterion: A brief text entry naming the in- and/or exclusion criterion (e.g. age, sex, atrial fibrillation)

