		Dissemination level: public

We will calculate crude incidence rate ratios (IRRs) for each event with 95% confidence intervals, for the vaccinated and COVID-19 cohorts compared against the background general population cohort. This will be done both overall and stratified by key factors including age, sex, prior COVID-19 diagnosis, prior vaccination status and whether patients are immunosuppressed. We will estimate the number of events expected among the vaccinated and COVID-19 cohorts using indirect standardisation by age and sex (with 10-year age bands), using the general population cohort as the standard population. We will calculate standardized incidence rate ratios (SIRs) and 95% confidence intervals comparing observed and expected rates. Rates will be reported overall, and by 10-year age bands, by sex, by prior COVID-19 diagnosis, by prior vaccination status and whether patients were immunosuppressed. A standardized incidence rate ratio above 1 will indicate that the observed rate for a specific outcome is higher than what is expected in the general background population.

Table 8: Primary, secondary, and subgroup analysis specification

A. Primary analysis

Hypothesis:	Objective 1 -3: Not applicable, descriptive incidence rate. Objective 4: use of intensive care services during a hospitalisation can be considered as key intermediate events between testing positive for SARS-COV-2 or having a clinical diagnosis of COVID-19 in an outpatient setting on the one end to a COVID-19-related death on the other. Objective 5: Covid-19 infection or vaccination may change the incidence rate of study events in population.
Exposure contrast:	Objective 1 -3: Not applicable, descriptive incidence rate. Objective 4: Not applicable, risk factor analysis Objective 5: Infected or vaccinated vs. the non-infected or non-vaccinated population
Outcome:	Objective 1 -3: Incidence rates of VTE, ATE Objective 4: VTE, ATE, death Objective 5: Incidence rates of VTE, ATE
Analytic software:	R

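### The protocol does not fix whether background-cohort members resume after an event; coded as section 8.4 reads, the reference rate is too low and the null SIR sits modestly above 1

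*Protocol*

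**What the plan says.** **Background cohort (cohort 1).** The text of section 8.4 reads: "For cohort 1, follow-up will begin on January 1st 2017 and continue up until the first of: outcome of interest, loss to follow-up, death", with 31 December 2019 as the last possible date. The Time row of Table X in section 7 repeats the stopping rule: "continue up until the first of: outcome of interest, loss to follow-up, death or December 31st 2019". Neither place says what happens after an event.

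Table 2 in section 8.4 anchors cohort 1 at 1 January 2017 "or after when they have 365 days of prior history". Its entry under number of entries is Multiple. The key below the table explains that column: "Indicate whether patients are allowed to enter the study population only once or multiple times". No event or date is given that would start a second entry.

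The main-measure row of Table X describes incidence over 30 to 180 days after index for the pre-pandemic cohort as well, and section 8.8.2 says the same of each cohort. That does not fit follow-up to the end of 2019.

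**Exposed cohorts (2 to 5).** Follow-up stops at whichever comes earliest: "outcome of interest, end of observation period, end of data availability, death, or either 30-, 60-, 90- or 180-days after the index date". Table 2 allows multiple entries, each with its own index date.

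**Outcome washout.** Table 4 in section 8.5 reads "Exclude people with the outcome of interests during the 183 day prior to index" and lists cohorts 1 to 5. The abstract agrees: "For all cohorts, individuals with recent VTE or ATE event" are excluded. Table 9 varies the washout to 91 days and to any history.

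**Use.** Section 8.8.5 obtains expected counts by indirect standardisation on age and sex, "using the general population cohort as the standard population", and reads an SIR above 1 as a rate higher than expected.

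**The concern.** An SIR is centred on 1 under no effect only if the observed and reference cohorts admit people on the same terms. Here the washout is relative to the index date. A person in cohorts 2 to 5 gets a new index date at each infection, admission or dose, so the screen is repeated, and anyone whose last event is more than 183 days old is eligible. Cohort 1 has one stated time anchor and up to three years of follow-up that stops at the outcome.

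Read literally, a person with a VTE in June 2017 gives no background time in 2018 or 2019. A person with the same history in 2021-22 is eligible for an exposed cohort about six months after the event. If recurrence, or re-recording of an old event, is more frequent than a first event, the reference is gradually depleted of its highest-rate members and the expected count is too low. Age and sex standardisation does not correct this. Section 11 says that outcomes will not be validated by case-note review, so re-recorded events can count, and its list of limitations does not mention this asymmetry.

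Objective 5 rests on the ratio. The shift would act in the same direction for infection and for every vaccine dose.

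**Working it through.** The protocol states no first-event rate, recurrence rate or expected SIR, so there is no figure of its own to reproduce. The check compares the possible readings of cohort 1 under no exposure effect.

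**Inputs from the protocol:** 183-day washout at index (91 days in a sensitivity analysis); exposed window 90 days; background follow-up 3 years (1 January 2017 to 31 December 2019).

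**Assumptions, not in the protocol:** one age-sex stratum in a steady state with population turnover of 1/15 per year; first-event rate λ of 1.5, 5 or 15 per 1000 person-years; recurrence or re-recording rate either constant at 2% or 5% per year, or falling with time since the event (under 1 year / 1 to 3 years / over 3 years) as 10/6/3, 20/10/4 or 40/20/5 % per year.

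**Method:** a day-step model with three states: no prior event; last event under 183 days ago (not eligible); last event at least 183 days ago (eligible). Null SIR = exposed 90-day rate / background 3-year rate.

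**Mechanism, worked by hand.** Let h be the share of person-time from people with an earlier event, and r a constant recurrence rate. Then rate = λ + h(r − λ). With λ = 5 and r = 50 per 1000:

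- Exposed: h = 0.0656, rate = 5 + 0.0656 × 45 = 7.95.
- Background, permanent exit: h averages 0.0562 over three years, rate = 5 + 0.0562 × 45 = 7.53.
- Null SIR = 7.95 / 7.53 = 1.06.

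The depletion is partial. People whose event was more than 183 days before entry remain in cohort 1, so h falls but does not reach zero.

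**Null SIR, permanent exit:**

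| Recurrence, % per year | λ = 1.5 | λ = 5 | λ = 15 |
|---|---|---|---|
| constant 2 | 1.02 | 1.02 | 1.01 |
| constant 5 | 1.06 | 1.06 | 1.04 |
| 10/6/3 | 1.09 | 1.08 | 1.07 |
| 20/10/4 | 1.16 | 1.15 | 1.14 |
| 40/20/5 (heavy re-recording) | 1.34 | 1.33 | 1.30 |

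Example: λ = 5 with 10/6/3 gives 7.17 exposed against 6.62 background per 1000 person-years; 7.17 / 6.62 = 1.08.

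**The other readings, same inputs:**

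- Cohort 1 re-enters after 183 event-free days: 0.98 to 1.00 up to 20/10/4, and 0.96 at 40/20/5. In the example, 7.17 / 7.23 = 0.99.
- Cohort 1 limited to the same 90-day window: 1.00.
- Any prior history excluded in both cohorts: 1.00.
- 91-day washout with permanent exit: the example rises from 1.08 to 1.09.
- Recurrence equal to the first-event rate: 1.00 throughout, as it should be.

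**Whether a few percent can show.** Table 1 lists 6,548,545 Pfizer records in SIDIAP. At an assumed 1.5 per 1000 person-years and 90 full days each, that is 6,548,545 × 90/365.25 × 0.0015 ≈ 2,420 events, and 1.96/√2,420 ≈ 4% either side. This pools all doses and ignores exclusions, so dose-specific estimates would be less precise.

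**The case against.** The strongest reply is that the protocol already contains the right rule in pieces. Table 2 gives cohort 1 multiple entries, and Table 4, Table 6 and the abstract apply the 183-day outcome washout to it. Put together, these amount to stopping at an event and resuming after the washout, and the upward shift disappears. Under Table X's shorter window it disappears too. Table 9 also plans an any-history analysis in which the asymmetry is absent, so a material distortion would show as a difference from the primary result.

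Much of this stands. A reader might infer from 8.4 that background members leave for good at their first-ever event. The protocol does not say so: it is the in-study event that ends follow-up, and Table 2 points the other way. Nor is it fixed that a person with an event in late 2016 is lost for all three years, because the order-of-application cell for prior outcomes in Table 4 is blank.

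A reader might also take the n/a under washout in Table 2 to mean re-entry with no event-free gap, and so a downward bias. That misreads the column. The key says it applies when entry is defined as incident, whereas entry to cohort 1 is general population, and the outcome washout is set elsewhere.

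What the reply does not supply is a resumption date. The stopping rule is explicit and stated twice; the re-entry rule has to be assembled from table cells with no trigger, and the third window agrees with neither. The any-history analysis can reveal a problem but does not repair the primary analysis.

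**Conclusion.** The point holds as an unreconciled contradiction with a measurable consequence, not as an established biased design. Three descriptions of cohort 1 person-time stand in the protocol, and they give different null SIRs: about 1.01 to 1.16 if the follow-up sentence is coded literally (about 1.3 only with heavy re-recording), 0.96 to 1.00 with 183-day re-entry, and 1.00 with a matched window.

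The direction under the literal reading needs only that recurrence or re-recording exceeds first incidence. The size rests wholly on assumed rates. It would be too strong to conclude that the reported SIR will exceed 1 without an exposure effect: section 11 accepts that only age and sex are standardised, and other differences between the periods could push either way. The matter should be settled before the code is run, because it sets the reference rate for Objective 5.

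**What to change.** In the Time row of Table X, section 8.4, Table 2 and Table 4, state one rule for cohort 1: a member stops contributing at an event and resumes after 183 consecutive event-free days, and a person with an event in the 183 days before 1 January 2017 (or before completing 365 days of history) first enters on reaching that gap. Use 91 days in the 91-day sensitivity analysis, and no return or entry after any event in the any-history one. Reconcile this with the 30- to 180-day window given for the pre-pandemic cohort in Table X and section 8.8.2. The n/a under washout in Table 2 can stay.

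The cost is protocol wording and a repeat-event setting with outcome washout in the cohort 1 code; no new data are needed. The downside is that a few people contribute more than one background event, so the background is no longer strictly one event per person.

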7. RESEARCH QUESTION AND OBJECTIVES

The aim of the study is to contextualise the risk of venous and arterial thromboembolic events associated with COVID-19, during the Omicron period and SARS-CoV-2 vaccination. To do so, the research objectives are:

1. To estimate the background incidence rate of venous and arterial thromboembolic events among the general pre-pandemic population.
2. To estimate the incidence rate of venous and arterial thromboembolic events among patients with COVID-19 within 30-, 60-, and 90- and 180-days during the Omicron period, stratified by prior SARS-CoV-2 vaccination and prior infection status.
3. To estimate the incidence rate of venous and arterial thromboembolic events among patients with SARS-CoV-2 vaccination within 30-, 60-, 90- and 180-days, stratified by prior infection status.
4. To estimate a) the association between clinical risk factors, including prior SARS-CoV-2 vaccination, on the incidence rate of venous and arterial events among people with COVID-19 and b) the impact that thromboembolic events have on worsening severity of COVID-19 during the Omicron period.
5. To estimate incidence rate ratios for venous and arterial thromboembolic events among patients with COVID-19 and different SARS-CoV-2 vaccine doses compared to the background population, using incidence rates estimated in objectives 1 to 3.

Table X: Primary and secondary research questions and objective

A. Primary research question and objective

Objective:	
 1. To estimate the background incidence rate of venous and arterial thromboembolic events among the general pre-pandemic population. 2. To estimate the incidence rate of venous and arterial thromboembolic events among patients with COVID-19 within 30-, 60-, and 90- and 180-days during the Omicron period, stratified by prior SARS-CoV-2 vaccination and prior infection status.
-------------------	---

	Phase II C3-001 – Study Protocol	
	Author(s): [name], [name]	Version: v3.1
	Dissemination level: public	

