Measurement characteristics/validation: If there are measurement characteristics for the outcome algorithm (e.g. PPV, sensitivity, specificity) from publications, or from outcome validation within the study population (e.g., medical record review), provide this information.

Source of algorithm: Specify the source of algorithms to define the time 0 or primary anchor criteria.

The table below further describes the operational definitions with regard to the follow-up start and the follow-up end.

Follow up start	Day 1	Index date
Follow up end¹	Select all that apply	Specify
Date of outcome	Yes	
Date of death	Yes	
End of observation in data	Yes	

	Phase II C3-001 – Study Protocol	
	Author(s): [name], [name]	Version: v3.1
	Dissemination level: public	

Day X following index date (specify day)	Yes	180 days after index date
End of study period (specify date)	Yes	End of data availability per database
End of exposure (specify operational details, e.g. stockpiling algorithm, grace period)	n/a	
Date of add to/switch from exposure (specify algorithm)	n/a	
Other date (specify)	n/a	

¹ Follow up ends at the first occurrence of any of the selected criteria that end follow up.

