 - whether the vaccination record is 1st, 2nd, 3rd or 4th dose. A 21 day gap between two consecutive records of vaccine will be required to avoid repeated records of the same vaccine. The 21-days period was chosen based on the minimal recommended dosing schedule of the primary vaccine course in participated databases (Spain).
 - have at least 365 days of data availability prior to index date

Cohorts 2 to 5 will be stratified by prior COVID-19 infection status and for cohorts 2 to 4 also by prior SARS-CoV-2 vaccination status. All cohorts will additionally be stratified by whether patients are immunocompromised on the index date. People in each of the five cohorts will be required to have at least a year of observed history in the database prior to their index date. This is to ensure a sufficient time period to identify health conditions and medication use prior to individuals' index dates.

	Phase II C3-001 – Study Protocol	
	Author(s): [name], [name]	Version: v3.1
		Dissemination level: public

Table 3. Operational Definitions of Inclusion Criteria

Criterion	Details	Order of application	Assessment window	Care Setting ¹	Code Type	Diagnosis position ²	Applied to study populations:	Measurement characteristics/validation	Source for algorithm
Observation period of 365day prior entry (all 5 cohorts)	Study participants will be required to have 365 days prior history observed before contributing observation time	before	[-365,0]	n/a	n/a	n/a	All individuals within the selected databases	n/a	n/a
Covid-19 infection (cohort 2)	have either a positive test result for SARS-CoV-2 or a clinical diagnosis of COVID-19 on or after 1 st December 2021 (with the index date being whichever date comes first if both occur)	before	n/a	Primary care	SNOMED	n/a	All individuals within the selected databases	n/a	n/a
Covid-19 hospitalized (cohort 3)	a hospitalisation on or after 1 st December 2021 (with the index date the date of hospital admission), a record of a clinical diagnosis of COVID-19 or a positive test result for SARS-CoV-2 in the period between 3 weeks prior to and up to 3 days following the index date	before	[-21, 3]	Primary care, secondary care	SNOMED	n/a	All individuals within the selected databases	n/a	n/a

	Phase II C3-001 – Study Protocol	
	Author(s): [name], [name]	Version: v3.1
	Dissemination level: public	

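### Follow-up runs on through later vaccine doses, COVID-19 and re-infection, so the dose-specific rates and SIRs do not isolate the dose, and no censored analysis is planned beside them

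*Protocol*

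**What the plan says.** Section 8.4 gives one stopping rule for cohorts 2 to 5: "For cohorts 2 to 5, follow-up will begin on their index date and continue up until the first of: outcome of interest". The full list is "outcome of interest, end of observation period, end of data availability, death, or either 30-, 60-, 90- or 180-days after the index date". The section 7 table repeats this rule for objectives 2 and 3 in almost the same terms.

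The follow-up end table in 8.4 agrees. The rows for end of exposure, for "Date of add to/switch from exposure" and for any other date are all marked not applicable. Its footnote reads: "Follow up ends at the first occurrence of any of the selected criteria that end follow up".

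Four other provisions bear on the point:

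- Table 2 in 8.4 allows multiple entries per person in every cohort, and 8.5 describes the five cohorts as not mutually exclusive.
- For vaccines, 8.5 says: "A 21 day gap between two consecutive records of vaccine will be required to avoid repeated records of the same vaccine". It bases the 21 days on the shortest recommended primary schedule.
- For infection, the Table 2 washout is "No covid-19 infection within 3 months prior". Table 4 writes it as [-91,0].
- Objective 5 in section 7 seeks ratios for COVID-19 patients and "different SARS-CoV-2 vaccine doses compared to the background population, using incidence rates estimated in objectives 1 to 3".

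**The concern.** Section 8.6.1 defines vaccine exposure by dose and brand, and objective 5 turns the resulting rates into ratios by dose. If dose 2 arrives inside the dose-1 window, what follows is dose-1 follow-up by label and dose-2 follow-up in fact. An event in that stretch counts under dose 1 and again under dose 2. Vaccine follow-up also continues through COVID-19, the other exposure the study aims to contextualise, so an event triggered by infection is credited to the vaccine.

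The rate ratios by dose, and any reading of vaccination beside infection, would then reflect mixed exposure. Carry-over tends to draw the dose-specific results towards each other. COVID-19 during follow-up would raise the vaccine SIR even if the vaccine had no effect.

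**Working it through.** The protocol gives no overlap or event figure to reproduce, so the check starts from its rules.

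**Inputs.** Windows w = 30, 60, 90 and 180 days (8.4). Minimum dose gap g = 21 days (8.5). Infection exclusion window [-91,0] (Table 4), so the earliest re-entry is day 92. The longer dose gaps below are assumptions, because the protocol gives no gap distribution.

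**1. Later-dose time inside the dose-1 window.** Share = max(0, w − g)/w for a person who receives dose 2 on day g.

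| Gap g | 30-day | 60-day | 90-day | 180-day |
|---|---|---|---|---|
| 21 (minimum) | 9/30 = 30.0% | 39/60 = 65.0% | 69/90 = 76.7% | 159/180 = 88.3% |
| 28 (assumed) | 6.7% | 53.3% | 68.9% | 84.4% |
| 56 (assumed) | 0% | 6.7% | 37.8% | 68.9% |
| 84 (assumed) | 0% | 0% | 6/90 = 6.7% | 96/180 = 53.3% |

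Read literally, the [-21,0] vaccine window in Table 4 puts the next dose at day 22 at the earliest. The first row then becomes 26.7, 63.3, 75.6 and 87.8%.

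**2. Events counted under two doses.** With doses 21 days apart, an event after day 21 and up to day 30 lies in the 30-day window of both doses. For the 180-day windows the shared stretch runs from day 21 to day 180. The 183-day outcome washout removes a person from the dose-2 cohort only if the event came before dose 2, so these later events are untouched.

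**3. Re-infection.** With re-entry from day 92, overlap is zero for the 30-, 60- and 90-day COVID-19 windows. For the 180-day window it is at most (180 − 92)/180 = 88/180 = 48.9%.

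**4. Illustrative effect on a dose-1 ratio.** Assume dose 1 has no effect, everyone gets dose 2 on day 21, and dose 2 doubles the rate for 30 days. Apparent dose-1 ratio = 1 + (2 − 1) × (raised-rate days in the window)/w:

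- 30-day: 1 + 9/30 = 1.30
- 60-day: 1 + 30/60 = 1.50
- 90-day: 1 + 30/90 = 1.33
- 180-day: 1 + 30/180 = 1.17

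**5. Illustrative effect of COVID-19 on a vaccine SIR.** Assume the vaccine has no effect, a share p is infected evenly over 180 days, and infection multiplies the rate by R for 30 days. The mean raised-rate time per infected person inside the window is (150 × 30 + 30 × 15)/180 = 27.5 days. SIR = 1 + p(R − 1) × 27.5/180:

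- p = 0.1, R = 3: 1.03
- p = 0.3, R = 10: 1.41

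**6. Interval width.** Within one dose a person has one index date and stops at the first outcome, so a single dose-specific rate holds at most one event per person. Repetition arises only when doses are pooled or a person re-enters a COVID-19 cohort. If every event in such an estimate were counted exactly twice, a Poisson standard error would be too small by a factor of √2 = 1.41.

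**7. Other provisions that might repair this.** Stratification in 8.5 uses status before the index date. Table 9 has no analysis that censors at a later exposure. Its washout row recognises that people must be event-free after earlier doses to enter later vaccine cohorts, but it does not deal with events after the later index. Section 11 does not mention overlapping windows.

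**The case against.** The strongest reply is that this is a deliberate and consistent choice. Section 7, section 8.4 and the follow-up end table agree, and objectives 1 to 3 are descriptive. The rate in the 30 to 180 days after dose k, whatever follows, is a legitimate quantity. That stands: a reader might infer that the protocol contradicts itself or forgot to censor, and neither is so. But the protocol never says that its dose-specific results carry that meaning, and it sits poorly with ratios by dose and brand and with the Table 8 contrast of infected or vaccinated people against those who are neither.

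Several stronger readings are tempting, and the documents do not support them:

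- **That 30 to 88% of dose-1 time is dose-2 time in these data.** These are ceilings that need every recipient to have dose 2 on day 21. The 21 days serves to remove duplicate records and reflects the shortest schedule. At an assumed 84 days the 30- and 60-day windows are untouched.
- **That the Poisson intervals are too narrow throughout.** Single dose-specific rates are unaffected. Overlap between two doses correlates two separate estimates and does not breach independence within either.
- **That re-infection distorts all COVID-19 windows.** Only the 180-day window is open to it, and a re-infected person remains COVID-exposed, so the issue is duplicated time more than mixed exposure.
- **That counting an event in the 30-, 60-, 90- and 180-day windows of the same index is an error.** Those windows are nested by design.
- **That censoring must replace the planned analysis.** Censoring at the next dose leaves later dose-1 time to people who delayed or never had dose 2. Censoring at recorded COVID-19 depends on testing, which 8.6.1 and section 11 say varied, and could drop thrombotic events first tested on admission. Either form may be informative.

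**Conclusion.** The concern holds in this form. Follow-up does not end at the next dose, at COVID-19 during vaccine follow-up or at re-infection. The dose-specific rates and SIRs therefore do not isolate the dose, and the vaccine results do not exclude events that follow infection. The problem is greatest for early doses in the longer windows.

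The overlap shares follow from the protocol's own minimum gaps and are upper limits. The actual bias depends on dose gaps, uptake and infection frequency, none of which the protocol gives. The shifts in apparent ratios (1.17 to 1.50 for dose 1, and 1.03 to 1.41 for the 180-day vaccine SIR) rest entirely on the stated assumptions and show only that the effect can be material. The variance problem is confined to estimates pooled over doses and to cohorts 2 to 4 with re-entry.

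**What to change.** In section 8.4, its follow-up end table and Table 9:

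- Add an analysis that censors cohort 5 at the next COVID-19 vaccine record and at a COVID-19 diagnosis or positive test.
- In the same analysis, censor cohorts 2 to 4 at a new COVID-19 episode and, as a sensitivity analysis, at vaccination.
- Report it beside the uncensored analysis for every dose-specific rate and SIR, with the share of overlapping person-time.
- Describe the uncensored result as the rate after dose k, whatever follows.
- Use person-clustered variance wherever one person contributes more than one entry to the same estimate.

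The cost is analysis code and a few lines of protocol text. The data are secondary, and section 5 still lists code creation and execution as to be confirmed. The downside should be stated in the protocol. Less dose-1 person-time remains beyond the usual dose gap: someone who has dose 2 on day 21 contributes at most 21 days to any of the four windows. The censoring may also be informative, which is why both versions are shown.
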